4.3 JUSTIFICATION FOR DOSE

The selected dosing regimen is dupilumab 300 mg Q2W with a loading dose of 600 mg.

This dose regimen is expected to achieve serum concentrations that saturate the target-mediated clearance pathway rapidly with the loading dose and maintain saturation thereafter. The PK of dupilumab is consistent across populations of patients with AD, asthma, CRSwNP, and EoE, as well as healthy volunteers. Furthermore, the sources of variability of dupilumab PK identified in each population and the magnitude of the covariate effects indicate that body weight is the most influential factor, whereas other covariates identified as being statistically significant have no meaningful impact on dupilumab PK. The immunogenicity of dupilumab is also comparable in these populations (see IB).

Dosing regimens of 300 mg Q2W after a loading dose of 600 mg were used in the PN case studies, which resulted in marked improvement in itch within three months and subsequently a notable improvement of the skin lesions (see [Section 2](#)).

The 300 mg Q2W dose, with loading dose, is the approved dose for AD and is an approved dose for asthma in the US and the EU.

Therefore, based on the totality of the data, dupilumab 300 mg Q2W (with loading dose) regimen is adequate for patients with PN and a further dose ranging study is not necessary to select a Phase 3 dose regimen.

4.4 END OF STUDY DEFINITION

A participant is considered to have completed the study if he/she has completed all phases of the study including the last visit.

The end of the study is defined as the date of the last visit of the last participant in the study.

5 STUDY POPULATION

Prospective approval of protocol deviations to recruitment and enrollment criteria, also known as protocol waivers or exemptions, is not permitted.

5.1 INCLUSION CRITERIA

Participants are eligible to be included in the study only if all of the following criteria apply:

Age

I 01. Participants must be 18 to 80 years of age, at the time of signing the informed consent.

Type of participant and disease characteristics

Patients with a clinical diagnosis of PN, as defined by all of the following:

I 02. Diagnosed by a dermatologist for at least 3 months before the Screening visit.

I 03. On the WI-NRS ranging from 0 to 10, patients must have an average worst itch score of ≥ 7 in the 7 days prior to Day 1.

NOTE: Baseline pruritus NRS average score for maximum itch intensity will be determined based on the average of daily NRS scores for maximum intensity (the daily score ranges from 0 to 10) during the 7 days immediately preceding randomization. A minimum of 4 daily scores out of the 7 days is required to calculate the baseline average score. For patients who do not have at least 4 daily scores reported during the 7 days immediately preceding the planned randomization date, randomization should be postponed until this requirement is met, but without exceeding the 28-day maximum duration of the screening period.

I 04. Patients must have a minimum of 20 PN lesions in total on both legs, and/or both arms and/or trunk, at Screening visit and on Day 1.

NOTE: Patients need to have bilaterally symmetrical lesions on the extremities. The presence of lesions on at least 2 body surface areas is required.

I 05. History of failing a 2-week course of medium-to-superpotent TCS or when TCS are not medically advisable.

NOTE: Failure is defined as patients who are unable to achieve and/or maintain remission and low disease activity (similar to IGA PN-S score of ≤ 2 [≤ 19 nodules]) despite treatment with a daily regimen of medium-to-superpotent TCS (\pm TCI as appropriate), applied for at least 14 days, or for the maximum duration recommended by the product prescribing information, whichever is shorter.

I 06. Have applied a stable dose of topical emollient (moisturizer) once or twice daily for at least 5 out of the 7 consecutive days immediately before Day 1 (NOTE: See exclusion criterion [E 20](#) for limitations regarding emollients; see background treatment with topical emollient in [Section 6.1.1](#)).

I 07. Participants must be willing and able to complete a daily symptom eDiary for the duration of the study.

Sex

I 08. Male or Female

Contraceptive use by women should be consistent with local regulations regarding the methods of contraception for those participating in clinical studies.

a) Female participants

- A female participant is eligible to participate if she is not pregnant or breastfeeding, and at least one of the following conditions applies:
 - Is not a WOCBP.

OR

 - Is a WOCBP and agrees to use a contraceptive method as described in Appendix 4 ([Section 10.4](#)) during the study (at a minimum until 12 weeks after the last dose of study intervention).
 - A WOCBP must have a negative highly sensitive ([Section 10.2](#)) pregnancy test (urine or serum as required by local regulations) on Day 1 before the first dose of study intervention.
 - If a urine test cannot be confirmed as negative (eg, an ambiguous result), a serum pregnancy test is required. In such cases, the participant must be excluded from participation if the serum pregnancy result is positive.
 - Additional details can be found in Appendix 4 ([Section 10.4](#)).
 - The investigator is responsible for review of medical history, menstrual history, and recent sexual activity to decrease the risk for inclusion of a woman with an early undetected pregnancy.

Informed Consent

I 09. Capable of giving signed informed consent as described in Appendix 1 ([Section 10.1](#)) of the protocol which includes compliance with the requirements and restrictions listed in the informed consent form (ICF) and in this protocol. In countries where legal age of majority is above 18 years, a specific ICF must also be signed by the participant's legally authorized representative.

5.2 EXCLUSION CRITERIA

Participants are excluded from the study if any of the following criteria apply:

Medical conditions

E 01. Presence of skin morbidities other than PN and mild AD that may interfere with the assessment of the study outcomes. Conditions such as, but not limited to, the following: scabies, insect bite, lichen simplex chronicus, psoriasis, acne, folliculitis, habitual picking, lymphomatoid papulosis, chronic actinic dermatitis, dermatitis herpetiformis, sporotrichosis, bullous disease.

NOTE: patients with mild active AD will represent up to 10% of the atopic PN study population.

E 02. PN secondary to medications (eg, opioids, angiotensin converting enzyme [ACE] inhibitors).

E 03. PN secondary to medical conditions such as neuropathy or psychiatric disease (eg, notalgia paresthetica, brachioradial pruritus, neurotic excoriations, obsessive compulsive disorder, delusions of parasitosis, etc).

E 04. Patients with a documented AD severity moderate to severe within 6 months before the screening visit, or documented diagnosis of moderate to severe AD from screening visit to randomization visit (eg, IGA AD of 3 or 4, eczema area and severity index [EASI] ≥ 16 , scoring atopic dermatitis [SCORAD] ≥ 25).

E 05. Severe concomitant illness(es) under poor control that, in the investigator's judgment, would adversely affect the patient's participation in the study. Examples include, but are not limited to patients with life expectancy shorter than 1 year, patients with uncontrolled diabetes (hemoglobin A1c $\geq 9\%$ according to the laboratory results within 3 months before screening visit), patients with cardiovascular conditions (eg, Class III or IV heart failure according to the New York Heart Association classification), hepato-biliary conditions (eg, Child-Pugh Class B or C), neurological conditions (eg, demyelinating diseases), active major autoimmune diseases (eg, lupus, inflammatory bowel disease, rheumatoid arthritis, etc), other severe endocrinological, gastrointestinal, metabolic, pulmonary, or lymphatic diseases. The specific justification for patients excluded under this criterion will be noted in study documents (chart notes, eCRF, etc).

E 06. Severe renal conditions (eg, patients with uremia and/or on dialysis).

E 07. Participants with uncontrolled thyroid disease.

E 08. Active TB or non-tuberculous mycobacterial infection, or a history of incompletely treated TB will be excluded from the study unless it is well documented by a specialist that the participant has been adequately treated and can now start treatment with dupilumab in the medical judgment of the investigator and/or infectious disease specialist. Tuberculosis testing will be performed on a country-by-country basis, according to local guidelines if required by regulatory authorities or ethics boards.

- E 09. Diagnosed active endoparasitic infections; suspected or high risk of endoparasitic infection, unless clinical and (if necessary) laboratory assessment have ruled out active infection before randomization.
- E 10. Active chronic or acute infection (except HIV infection) requiring treatment with systemic antibiotics, antivirals, antiprotozoals, or antifungals within 2 weeks before screening visit or during the screening period.
- E 11. Known or suspected immunodeficiency, including history of invasive opportunistic infections (eg, TB, histoplasmosis, listeriosis, coccidioidomycosis, pneumocystosis, aspergillosis) despite infection resolution, or otherwise recurrent infections of abnormal frequency or prolonged duration suggesting an immune-compromised status, as judged by the investigator.
- E 12. Active malignancy or history of malignancy within 5 years before the baseline visit, except completely treated in situ carcinoma of the cervix, completely treated and resolved non-metastatic squamous or basal cell carcinoma of the skin.
- E 13. History of systemic hypersensitivity or anaphylaxis to any biologic therapy, including any excipients.
- E 14. Any other medical or psychological condition including relevant laboratory abnormalities at screening that, in the opinion of the investigator, suggest a new and/or insufficiently understood disease, may present an unreasonable risk to the study patient as a result of his/her participation in this clinical trial, may make patient's participation unreliable, or may interfere with study assessments. The specific justification for patients excluded under this criterion will be noted in study documents (chart notes, eCRF, etc).
- E 15. History of substance and/or alcohol abuse.
- E 16. Planned major surgical procedure during the patient's participation in this study.

Prior/concomitant therapy

- E 17. Exposure to another systemic or topical investigative drug (monoclonal antibodies as well as small molecules) within a certain time period prior to Visit 1 (screening), as follows: an interval of less than 6 months or <5 PK half-lives for investigative monoclonal antibodies, whichever is longer, and an interval of less than 30 days or <5 PK half-lives, whichever is longer, for investigative small molecules.
- E 18. Having used any of the following treatments within 4 weeks before the screening visit
 - Systemic immunosuppressive/immunomodulating drugs (eg, systemic corticosteroids, cyclosporine, mycophenolate-mofetil, interferon gamma, Janus kinase inhibitors, azathioprine, methotrexate, hydroxychloroquine, dapsone, sulfasalazine, colchicine, etc),
 - Intralesional corticosteroid injections and cryotherapy,
 - Phototherapy, including tanning beds,

- Naltrexone or other opioid antagonist,
- Gabapentin, pregabalin, and thalidomide.

Or starting to use the following treatments or changed the dose of the following treatments in 3 months before the screening visit or expected the dose of the following treatments will be changed throughout the study:

- Paroxetine, fluvoxamine, or other selective serotonin reuptake inhibitors (SSRIs),
- Serotonin and norepinephrine reuptake inhibitors (SNRIs),
- Amitriptyline or other tricyclic or tetracyclic antidepressants.

E 19. Previous treatment with biologic medicines within the following timeframe:

- Any cell-depleting agents including but not limited to rituximab: within 6 months before the screening visit,
- Omalizumab: within 5 months before screening visit,
- Other immunomodulatory biologics: within 5 half-lives (if known) or 16 weeks before the screening visit, whichever is longer.

E 20. Initiation of treatment with prescription moisturizers or moisturizers containing additives such as ceramide, hyaluronic acid, urea, menthol, polidocanol, or filaggrin degradation products during the screening period (patients may continue using stable doses of such moisturizers if initiated before the Screening visit).

E 21. Initiation of treatment with TCS/TCI (any potency) during the screening period or treatment with high potency or superpotent TCS/TCI during the screening period.

E 22. For participants who were on a stable regimen of TCS/TCI (maintain same medicine, same dose from 2 weeks prior to screening visit) at the screening visit:

- Application of TCS/TCI on fewer than 6 days during the 7 days immediately preceding randomization,
- Application of TCS/TCI of incorrect potency within 7 days before Day 1 according to the requirements of [Section 6.1.1](#), ie, low potency if on low potency at screening visit and medium potency if on medium or higher potency at screening visit.

E 23. Treatment with a live (attenuated) vaccine within 4 weeks before the screening visit.

NOTE: For patients who have vaccination with live, attenuated vaccines planned during the course of the study (based on national vaccination schedule/local guidelines), it will be determined, after consultation with a physician, whether the administration of vaccine can be postponed until after the end of study, or preponed to before the start of the study, without compromising the health of the patient:

- Patient for whom administration of live (attenuated) vaccine can be safely postponed would be eligible to enroll into the study,

- Patients who have their vaccination preponed can enroll in the study only after a gap of 4 weeks following administration of the vaccine.

E 24. Planned or anticipated use of any prohibited medications and procedures during screening and study treatment period.

Prior/concurrent clinical study experience

E 25. Participation in prior dupilumab clinical study; treated in the past with dupilumab; prior use of biologics for PN.

Diagnostic assessments

E 26. For participants without history of HIV infection before screening visit, positive HIV serology at screening.

For participants with history of HIV infection with CD4+ counts ≤ 300 cells/ μ L and/or detectable HIV viral load at screening.

E 27. Participants with any of the following result at screening:

- Positive (or indeterminate) HBs Ag or,
- Positive total HBc Ab confirmed by positive HBV DNA or,
- Positive HCV Ab confirmed by positive HCV RNA.

Other exclusions

E 28. Individuals accommodated in an institution because of regulatory or legal order; prisoners or subjects who are legally institutionalized.

E 29. Any country-related specific regulation that would prevent the subject from entering the study - see [Section 10.10](#) (country-specific requirements).

E 30. Participant not suitable for participation, whatever the reason, as judged by the Investigator, including medical or clinical conditions, or participants potentially at risk of noncompliance to study procedures.

E 31. Participants are dependent on the Sponsor or Investigator (in conjunction with Section 1.61 of the International Council for Harmonisation (ICH) good clinical practice (GCP) Ordinance E6).

E 32. Participants are employees of the clinical study site or other individuals directly involved in the conduct of the study, or immediate family members of such individuals.

E 33. Any specific situation during study implementation/course that may raise ethics considerations.

E 34. Sensitivity to any of the study interventions, or components thereof, or drug or other allergy that, in the opinion of the Investigator, contraindicates participation in the study.

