6.1.1 Noninvestigational medicinal products

Starting from the screening visit, participants will be instructed to use their daily moisturizer, if it is not containing any compound with known anti-itch effect (such as menthol, polidocanol, pramoxine, lidocaine, prilocaine, capsaicin, naltrexone, N-palmitoylethanolamine, etc). It is not authorized changing emollients or moisturizers or applying products for itching relief during the course of the study.

Participants will be required to apply moisturizers (emollients) once or twice daily for at least 5 out of the 7 consecutive days immediately before Day 1 and continue until Week 36. All types of moisturizers are permitted, but patients may not initiate new treatment with prescription moisturizers or over-the-counter moisturizers containing additives during the screening period or during the intervention period. Patients may continue using stable doses of such moisturizers if initiated before the screening visit.

If participants are on a stable regimen of low to medium potency TCS or TCI at the screening visit, they can continue their topical steroid application once daily without tapering from Screening to Week 24. If specific lesions resolve, the participant can stop applying steroids to those sites but are permitted to continue applying to persistent lesions. If participants are on stable regimens of high potency or superpotent steroids, participants should decrease potency to medium potency TCS and continue to apply daily from screening to Week 24. Stable regimen for TCS is maintaining the same medicine (low to medium potency TCS), and maintaining the same frequency of treatment (once or twice daily) used from 2 weeks prior to screening. Stable regimen for TCI is maintaining the same medicine of TCI and the treatment frequency (once or twice daily) used from 2 weeks prior to screening. If participant's prior regimen was applying once daily, the participant will maintain daily application during study and for participants who had twice daily prior to screening, participation will maintain twice daily regimen during study. If specific lesions resolve, the participant can stop applying steroids to those sites but are permitted to continue applying to persistent lesions. Occlusion is not allowed from Screening to Week 24.

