5.7 APPENDIX 7 MEDICATION/PROCEDURE ADJUDICATION ALGORITHM

Algorithm for determining whether treatment with following medications or procedures constitutes treatment failure resulting in setting data as non-responder after taking medication or undergoing procedure in the main statistical analysis

1. Not required to adjudicate post-baseline medications (WHODD-coded) or procedures (CMQ-coded) as these will be considered treatment failures if used at any time¹.
 - a) Always considered treatment failure
 - ATC2 = CORTICOSTEROIDS FOR SYSTEMIC USE
 - ATC2=IMMUNOSUPPRESSANTS (systemic, eg, oral or parenteral route)
 - Preferred Drug Name = Ciclosporin
 - Preferred Drug Name = Methotrexate
 - Preferred Drug Name = Mycophenolate sodium
 - Preferred Drug Name = Mycophenolic acid
 - Preferred Drug Name = Azathioprine
 - Preferred Drug Name = Gabapentin
 - Preferred Drug Name = Pregabalin
 - Preferred Drug Name = Thalidomide
 - Preferred Drug Name = Lenalidomide
 - Preferred Drug Name = Baricitinib
 - Preferred Drug Name = Ruxolitinib
 - Preferred Drug Name = Tofacitinib
 - Preferred Drug Name = AbrocitinibPreferred Drug Name = Delgocitinib
 - Preferred Drug Name = Nalbuphine
 - Preferred Drug Name = Naltrexone
 - Preferred Drug Name = Naloxone
 - Preferred Drug Name = Vixarelimab
 - Preferred Drug Name = Nemolizumab
 - Preferred Drug Name = Serlopitant
 - Preferred Drug Name = Aprepitant
 - CMQb HLT Phototherapies
 - CMQ Tanning_single PT
 - b) Never considered treatment failure:
 - ATC2 = EMOLLIENTS AND PROTECTIVES

- ATC2 = GENERAL NUTRIENTS
- ATC2 = VITAMINS
- ATC2 = ANTIVIRALS FOR SYSTEMIC USE
- ATC2 = ANTIFUNGALS FOR DERMATOLOGICAL USE
- ATC2 = ANTISEPTICS AND DISINFECTANTS
- ATC2 = ANTIBIOTICS AND CHEMOTHERAPEUTICS FOR DERMATOLOGICAL USE
- ATC2 = ANTI-ACNE PREPARATIONS, excluding D10AA Corticosteroids, combinations for treatment of acne
- ATC2 = OPHTHALMOLOGICALS
- ATC1 = ANTIINFECTIVES FOR SYSTEMIC USE, excluding D07C Corticosteroids, combinations with antibiotics
- ATC1 = BLOOD AND BLOOD FORMING ORGANS
- ATC1 = ALIMENTARY TRACT AND METABOLISM
- ATC1 = MUSCULO-SKELETAL SYSTEM, excluding M01BA Antiinflammatory/antirheumatic agents in combination with corticosteroids
- ATC2 = COUGH AND COLD PREPARATIONS
- ATC2 = PSYCHOLEPTICS, excluding N05BB Diphenylmethane derivatives and N05C HYPNOTICS AND SEDATIVES

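### E 20 and Section 6.1.1 conflict on continuing a menthol or polidocanol moisturizer, and the SAP does not count a newly started emollient-coded anti-itch product as treatment failure

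*Protocol*

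**What the plan says.** **Protocol 5.2, E 20** excludes a patient who starts, during screening, a prescription moisturizer or "moisturizers containing additives such as ceramide, hyaluronic acid, urea, menthol, polidocanol, or filaggrin degradation products during the screening period". It then adds that "patients may continue using stable doses of such moisturizers if initiated before the Screening visit".

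**Protocol 6.1.1, first paragraph**, on the product used once screening begins: "participants will be instructed to use their daily moisturizer, if it is not containing any compound with known anti-itch effect (such as menthol, polidocanol", followed by other named compounds. The next sentence reads: "It is not authorized changing emollients or moisturizers or applying products for itching relief during the course of the study".

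**Protocol 6.1.1, second paragraph**: "All types of moisturizers are permitted, but patients may not initiate new treatment with prescription moisturizers" or additive-containing ones in the screening or intervention period. It repeats the E 20 allowance for stable products begun earlier, and makes moisturizer use mandatory from before Day 1 to Week 36.

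**Protocol 5.1, I 06** requires stable emollient use on at least 5 of the 7 days before Day 1 and refers the site to both E 20 and 6.1.1.

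**SAP Table 5** lists the prohibited and rescue treatments that make a participant a non-responder. Topical itch-relief products have no row, although naltrexone, one of the 6.1.1 compounds, does. **SAP 5.7 (Appendix 7), item 1b**, includes "ATC2 = EMOLLIENTS AND PROTECTIVES" among the classes that are never a treatment failure.

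**The concern.** The primary endpoint is a fall of at least 4 points in worst itch at Week 24, so background anti-itch treatment bears on it directly. There are two separate problems.

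The first is the eligibility and background-treatment text. A patient who arrives on a menthol moisturizer may keep it under one passage and may not use it under another. What the site decides can affect the itch scores that determine entry (I 03, mean of at least 7) and the baseline from which the 4-point fall is measured.

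The second is the SAP. The protocol forbids applying itch-relief products during the study, but the rules for non-responders do not carry that prohibition through to products coded as emollients. A participant with uncontrolled itch who starts such a product after baseline, and improves on it, stays in the responder count.

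**Working it through.** No stated figure depends on this point, so the check is a comparison of passages.

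**A. The protocol conflict, for a patient on a stable menthol or polidocanol moisturizer begun before screening**

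1. E 20: not excluded; may continue.
2. 6.1.1, second paragraph: may continue; every type is allowed.
3. 6.1.1, first paragraph: the daily product may be used only if free of anti-itch compounds, and these two are named. This patient's product fails the condition.
4. The same paragraph does not authorize a change of moisturizer, while I 06 and the second paragraph require that one be used.
5. I 06 refers to both sections and does not say which prevails. Treating the first paragraph as the specific rule that overrides a general one does not settle it, because E 20 names the same two compounds.

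**B. What the conflict can reach**

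1. Screening lasts 2 to 4 weeks (14 to 28 days). I 03 and the WI-NRS baseline both use the 7 days before randomization.
2. If a site stops the product at the screening visit, the patient has been off it for 14 − 7 = 7 to 28 − 7 = 21 days when the baseline window opens. If a site lets it continue, baseline is measured on the product.
3. Two sites can thus record different qualifying scores and baselines for the same kind of patient. Randomization is stratified by atopy, TCS/TCI use and country, not by site or moisturizer type.

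**C. The SAP route, for a product newly started after baseline**

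1. Table 5: no row for topical anti-itch products. Of the compounds named in 6.1.1, only naltrexone appears, and it is also in the always-failure list of Appendix 7 item 1a.
2. Appendix 7 item 1b: if the product is coded as an emollient or protective, it is never a failure.
3. Appendix 7 item 2: adjudication covers other protocol-listed treatments given for PN-consistent indications, but only those not already placed under item 1. An emollient-coded product has been placed there.
4. Appendix 7 footnote 1: a blinded review may depart from the item 1 classes, but it is optional.
5. SAP 5.3 reports moisturizer compliance as days used over days in the period. It does not capture composition.

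Result: the prohibited start has no required route to non-responder status.

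**D. Scale.** With 75 per arm, each participant whose status changes moves that arm's response rate by 1/75 = 1.3 percentage points. The documents do not say how many participants use or start such products, so this is a unit of scale and not an estimate.

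**The case against.** - **Stable use is not a bias.** A product begun before screening and kept is constant background treatment, balanced in expectation by blinded randomization. This stands. A reader might infer a bias between arms from the contradiction; the documents do not support that.
- **On starting a product, the protocol is clear.** 6.1.1 forbids applying itch-relief products and starting prescription or additive-containing moisturizers. This stands too: the post-baseline problem is the SAP's failure to act on that prohibition, not a consequence of the contradiction.
- **The SAP is not empty here.** Naltrexone is covered, and item 2 may reach anti-itch products that are not coded as emollients. How pramoxine, lidocaine or capsaicin products would be coded is not shown. Protocol 6.5.1 and SAP 5.3 also commit to a blinded review of all post-baseline medications. This narrows the gap without closing it: that review is to adjudicate rescue, defined there as high-potency or superpotent TCS and TCI, and the override of item 1 remains optional.
- **The instructions might all be satisfied.** A reader might infer that a menthol user cannot meet them at all. That depends on reading the ban on changing moisturizer to cover a switch made at the screening visit. E 20 and the second paragraph bar only new prescription or additive-containing products, so they do not bar starting a plain moisturizer. The text is contradictory and unclear, but impossibility is not established.

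**Conclusion.** Two limited findings hold. First, E 20 and the second paragraph of 6.1.1 contradict the first paragraph of 6.1.1 on menthol and polidocanol moisturizers begun before screening. The likely effect is variation between sites in background itch treatment, eligibility scores and baseline WI-NRS, with no expected imbalance between arms. Second, a participant who newly starts an emollient-coded anti-itch product after baseline can still be counted as an itch responder, unless the optional review intervenes.

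The size cannot be quantified, because the documents give neither the frequency of use nor the effect of these products on WI-NRS. A reader might infer a placebo response raised by several percentage points; nothing in the documents supports a figure. If such starts were more common on placebo, the difference between arms would shrink, costing power rather than creating a false positive.

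The second finding assumes that the product is recorded as a concomitant medication and coded to the emollient class. Which clinical rule should apply is not judged here.

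**What to change.** **Protocol.** Reconcile E 20, I 06 and both paragraphs of 6.1.1 into one rule on moisturizers containing an anti-itch compound and begun before screening. State how that rule fits with the I 06 requirement and the ban on changing moisturizer. The choice of rule belongs to the sponsor.

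**SAP, before lock.**

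1. Add a Table 5 row for topical anti-itch products newly started after baseline, using the 6.1.1 compound list and marked for medical adjudication (footnote d).
2. In Appendix 7 item 1b, except those same newly started products from the emollient class, as other bullets in that list already do for their own exceptions. Confine the exception to new starts, so that stable use begun before screening is not reclassified.

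**Cost.** The SAP changes add a few records to the blinded review already planned and may make a few more participants non-responders. Protocol 6.5 already requires over-the-counter medicines to be recorded with reason and dates. The protocol change needs IRB/IEC approval (Section 10.1.1) and will come late for many participants, since the SAP dates the first randomization to 2 January 2020. The SAP changes remain useful until lock.
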